CLINICAL TRIAL PROTOCOL

Effects of Hippotherapy on Physical Fitness and Attention in Cerebral Palsy

NCT no.: NCT03870893

Protocol ID: 2017-0665-000

Date of the document: July 26, 2017

The purpose of this study

This research analyzes whether hippotherapy improves the physical activity, cardiopulmonary fitness, and attention in children with cerebral palsy and whether this enhances their general health and quality of life.

Background

This research aims to promote hippotherapy by scientifically proving its therapeutic effects and mechanism to contribute to improving the health and quality of life of the patients^{1,2} as well as reducing their global burden of disease by shifting the current passive “therapy-oriented” paradigm to a more proactive “participation-oriented” paradigm³.

Ever since physical activity and physical fitness have been reported to have an inverse relationship with the mortality rate, especially deaths due to cardiovascular disease, various efforts have been made to optimize physical activity and physical fitness among children with cerebral palsy⁴. ADHD is one of the most common coexisting conditions of cerebral palsy. More participation in engaging sports activities like therapeutic riding is anticipated to improve patient health and their quality of life⁵.

Hippotherapy is expected to improve clinical symptom of ADHD in children with cerebral palsy while preventing possible ensuing psychiatric disorders, thereby bringing significant improvement in their health and quality of life.

PARTICIPANTS

Forty-six children with CP (24 boys and 22 girls) participated in this study. Inclusion criteria were (a) diagnosis of CP, (b) classified at Gross Motor Function Classification System (GMFCS) level I -III, (c) body weight under 35kg, (d) ability to walk independently with or without an assistive device, (e) ability to comply with the study protocol and follow verbal directions. Exclusion criteria were (a) injected a botulinum

toxin within 3 months, (b) a selective dorsal rhizotomy or orthopedic surgery within 1 year, (c) moderate to severe intellectual disability(difficulty performing one step instructions), (d) uncontrolled seizures, (e) poor visual or acuity hearing impairment, (f) patients who weigh more than 35 kg, (g) hip dislocation, (h) scoliosis cobb angle > 30 degrees, (i) musculoskeletal surgery within 1 year.

INTERVENTION

Children allocated in the Hippotherapy group participated the Hippotherapy program in indoor riding arena. 23 children participated in the Hippotherapy program for 40 minutes per lesson twice a week for 16 weeks (total of 32 sessions). The sessions were conducted by three therapeutic riding instructors. One leader and two side walkers walked with a horse, and all participants wore helmets. Three participants were grouped together for each session. The Hippotherapy program sessions consisted of exercises to facilitate correct posture and balance, including lower extremity strengthening, and basic riding skills while walking and trotting. The intensity of the exercises and degree of assistance were individualized according to the participants' ability to control their body and horse. The horse/ponies had a height of 110-125-cm and weight of 250-400kg; all animals were very experienced in the Hippotherapy settings.

Statistical Analysis

Analyses were performed with SPSS version 20.0 (SPSS Inc, Chicago, IL, USA), using a .05 level of significance for all statistical tests. All continuous variables were tested for normality using the Shapiro–Wilk descriptive test. Means and standard deviations are presented for each continuous variable. After certification of the normality by the Shapiro Wilks test, the independent t-tests or Mann Whitney U-test were performed to examine the differences between the groups.

RERERENCE

1. Kwon, J. Y., Chang, H. J., Yi, S. H., Lee, J. Y., Shin, H. Y., & Kim, Y. H. (2015). Effect of hippotherapy on gross motor function in children with cerebral palsy: a randomized controlled trial. *The Journal of Alternative and Complementary Medicine*, 21(1), 15-21.
2. Kwon, J. Y., Chang, H. J., Lee, J. Y., Ha, Y., Lee, P. K., & Kim, Y. H. (2011). Effects of hippotherapy on gait parameters in children with bilateral spastic cerebral palsy. *Archives of physical medicine and rehabilitation*, 92(5), 774-779.

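### The unadjusted between-group test ignores age and GMFCS level although eligibility sets no age limits and spans levels I to III; this costs power if final, non-age-normed scores are compared, and little once baseline is used.

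*Combined protocol and SAP*

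**What the plan says.** The PARTICIPANTS section gives the sample: "Forty-six children with CP (24 boys and 22 girls) participated in this study". Severity and size are bounded by the opening of the eligibility list: "Inclusion criteria were (a) diagnosis of CP, (b) classified at Gross Motor Function Classification System (GMFCS) level I -III, (c) body weight under 35kg". Neither the five inclusion criteria nor the nine exclusion criteria state a minimum or maximum age. Children must also be able to walk, with or without a device, and to follow verbal directions.

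On allocation, the INTERVENTION section says only: "Children allocated in the Hippotherapy group participated the Hippotherapy program in indoor riding arena". It gives the size of that group ("23 children participated in the Hippotherapy program for 40 minutes per lesson twice a week for 16 weeks") but no allocation method, ratio or stratification. The size of the comparison group is not stated.

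The Statistical Analysis section tests each outcome "using a .05 level of significance for all statistical tests". After a normality check, "the independent t-tests or Mann Whitney U-test were performed to examine the differences between the groups". It names no covariate. It does not say whether final values, changes from baseline or age-normed scores are compared. No instrument is named for any outcome, and there is no sample-size calculation.

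**The concern.** The stated purpose covers physical activity, cardiopulmonary fitness and attention. In childhood, fitness and attention scores can be expected to vary with age, and activity and fitness with GMFCS level. A two-sample test with no covariates leaves all of that between-child spread in its error term. With about 23 children per group there is little precision to spare: the unadjusted t-test has 80% power only for a difference of about 0.84 SD. If age and severity explain a good part of the outcome variance and the analysis ignores them, a real benefit may be missed for want of two variables, one of which (GMFCS level) must be known at entry. The reader also cannot tell which ages the result applies to.

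**Working it through.** The plan has no power figure to reproduce.

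**Inputs from the documents.** 46 children in total and 23 in the hippotherapy group, so 46 − 23 = 23 in the comparison group (inferred). Significance level 0.05, taken as two-sided because the plan does not say.

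**Assumed inputs (none are in the documents).** True effect 0.7 SD, with residual SD 1 once age or level is known; no dropout; ages uniform from 4 to 14; outcome slope 0.1 to 0.4 SD per year; 15/15/16 children at GMFCS I/II/III; 0.4 to 0.8 SD per level.

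**Age, final scores compared.** Uniform ages over 10 years have variance 10²/12 = 8.33. The SD that the unadjusted test sees is √(1 + slope² × 8.33), and the standardised effect is d = 0.7 / that SD. Power comes from the noncentral t with 44 df and noncentrality d × √(23/2).

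| Slope per year | SD | d | Power, formula | Power, simulated |
|---|---|---|---|---|
| 0.1 | √1.083 = 1.041 | 0.673 | 61% | 60% |
| 0.2 | √1.333 = 1.155 | 0.606 | 52% | 52% |
| 0.3 | √1.750 = 1.323 | 0.529 | 42% | 41% |
| 0.4 | √2.333 = 1.528 | 0.458 | 33% | 32% |

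With age in the model the residual SD returns to 1 and d to 0.7. The formula gives 64%. Simulation gives about 62% to 63%, a little lower because age and group are correlated by chance. The loss is therefore about 2 points at the shallowest slope and about 30 at the steepest.

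**Severity, final scores compared.** For 15/15/16, the level coded 1 to 3 has variance 0.673. Fitting I-II v III leaves only the spread between I and II: 30 × 0.5² / 46 = 0.163.

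- 0.8 SD per level, unadjusted: SD √(1 + 0.64 × 0.673) = 1.196, d = 0.585, power 49%. With the stratum: SD √(1 + 0.64 × 0.163) = 1.051, d = 0.666, power 60% by formula and 59% by simulation.
- 0.4 SD per level, unadjusted: SD √(1 + 0.16 × 0.673) = 1.052, d = 0.665, power 60%. With the stratum: SD √(1 + 0.16 × 0.163) = 1.013, d = 0.691, power 63% by formula and 62% by simulation.

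**If a baseline score is used.** The same age model (slope 0.3) and severity model (0.8 SD per level) were simulated with an assumed within-age, or within-level, baseline-to-final correlation of 0.5 or 0.7.

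| Analysis | Correlation 0.5 | Correlation 0.7 |
|---|---|---|
| Change score, no age | 65% | 86% |
| Change score plus age | 64% | 85% |
| ANCOVA, no age | 71% | 88% |
| ANCOVA plus age | 75% | 89% |
| ANCOVA, no GMFCS | 71% | 88% |
| ANCOVA plus GMFCS | 73% | 88% |

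In the change score the age term cancels, because it is the same at both visits, so adding age gains nothing. In ANCOVA the baseline value already carries most of the age and severity information. Across these cases, and at a correlation of 0.6, the further gain is about 0 to 5 points.

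**Chance imbalance.** Suppose a simple random 23/23 split with 16 level III children. The number of them in one group is hypergeometric (46, 16, 23). The between-group gap must be even, so 5 or more means 6 or more: probability 12%. With 10 level III children it is 7%. The chance that at least one of the three levels differs by 5 or more is about 37% for a near-even split and 24% for 20/14/12, but that is a different event from a surplus at level III.

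**The case against.** Much of the case on the other side stands.

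- A reader might infer that allocation was not stratified and that raw scores are pooled. The documents support neither. They are silent on the whole allocation method and on the score scale; change scores or age-normed scores would fit the wording equally well.
- A reader might take the loss of 20 to 30 points at the steeper age slopes as separate from, and additional to, the benefit of using baseline values. It is not: the table above shows that most of it disappears once baseline enters the analysis.
- A reader might infer that the groups are probably unbalanced on severity and the comparison therefore biased. For level III the chance of a gap of 5 or more is about 12% under the assumed mix. Under random allocation such gaps add variance that the test's error rate already allows for. If allocation was not random, which the text leaves open, imbalance could be larger, but nothing in the documents shows that it was.
- A reader might infer that very young children could not do the tests. The walking, compliance and instruction-following criteria bound the sample functionally, and with no test named the matter cannot be judged.
- A broad GMFCS range is a legitimate choice for generalisability, and the past tense of the document suggests that enrolment and allocation are finished, so new eligibility or stratification rules would probably come too late.

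What survives is narrower. The only between-group analysis described takes no covariates, and nothing in the plan commits to a score that would remove age and severity spread.

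**Conclusion.** The point holds in conditional form. No age limits are stated, GMFCS I to III is eligible, no stratification is described, and the between-group tests are unadjusted. If final, non-age-normed scores are what is compared, ignoring age costs between about 2 and 30 points of power over the assumed slopes, and ignoring severity costs about 2 to 10 points over the assumed level effects. If change scores or baseline ANCOVA are used, what remains to be gained is about 0 to 5 points. Every magnitude rests on assumed effect size, age range, slope, level effect and GMFCS mix, and on an inferred second group of 23; only the direction follows from the documents. This is a loss of precision and a gap in specification, not a demonstrated bias.

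**What to change.** Replace the unadjusted between-group test with a linear model prespecified for each outcome, containing:

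- treatment group;
- age, or an age-standardised score as the outcome where norms exist;
- GMFCS stratum (I-II v III);
- the baseline value of the outcome, where it was measured.

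State which score is analysed for each outcome. Report the age range of the children enrolled and the allocation method actually used, including any stratification.

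Age and GMFCS stratum together cost about 2 degrees of freedom, taking the residual from 46 − 2 = 44 to 42. At d = 0.7 that alone changes power by about 0.1 point (64.1% to 64.0%). GMFCS level is an entry criterion and age should be on record, so no new data collection is expected. The model can still be adopted if allocation is already complete, provided it is fixed before outcomes are compared by group; otherwise it should be labelled as post hoc.

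### Does delivering hippotherapy to three children at a time invalidate the planned t-test or Mann-Whitney comparison?

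*Combined protocol and SAP*

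**What the plan says.** The Participants section gives the total: "Forty-six children with CP (24 boys and 22 girls) participated in this study". Under Intervention, "23 children participated in the Hippotherapy program", with two lessons a week for 16 weeks, or 32 sessions. On delivery it says "Three participants were grouped together for each session", that three riding instructors ran the sessions, and that "One leader and two side walkers walked with a horse". It adds "The intensity of the exercises and degree of assistance were individualized" to each child's control of body and horse.

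The Statistical Analysis section states that "the independent t-tests or Mann Whitney U-test were performed to examine the differences between the groups", "using a .05 level of significance for all statistical tests". No term for riding group, session or instructor appears.

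The text does not say how the threes were made up, whether they stayed the same over the 32 sessions, how children were matched to instructors, or whether comparison children did anything in groups.

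**The concern.** Both planned tests treat the 46 children as independent. Children treated together may share a lesson atmosphere, peers, a time slot and an instructor. If that sharing moves their outcomes together, the hippotherapy mean rests on fewer independent pieces of information than 23. The standard error is then too small, and a nominal .05 test rejects too often. Clustering in one arm only is a recognised feature of group-delivered therapy, so a plan that describes group sessions and then names only a two-sample test invites the question. At stake is whether a result just below .05 means what it says. The inflation would be symmetric and would not favour hippotherapy in particular.

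**Working it through.** **Inputs.** From the documents: 46 children, 23 in hippotherapy, so 46 − 23 = 23 in comparison; groups of three; 32 sessions; alpha .05 (taken as two-sided, since sidedness is not stated). Assumed, because the documents give no figure: the ICC, normal outcomes, an ungrouped comparison arm, and 7 trios plus 1 pair, because 23 is not a multiple of 3.

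**Plan's own figure.** The only figure to reproduce is alpha. With 23 v 23 independent children, simulation gives 5.0% for the t-test and 5.0% for the Mann-Whitney test.

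**Case 1: fixed trios with a shared effect.**
- Weighted group size = Σm²/Σm = (7×9 + 4)/23 = 67/23 = 2.913.
- Design effect in the hippotherapy arm, DE = 1 + 1.913 × ICC.
- Variance ratio for the mean difference = (DE + 1)/2, because only one arm is clustered.
- Approximate type I error = 2 × [1 − Φ(1.96/√ratio)].

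| ICC | DE | Variance ratio | True SE / naive SE | Approx. error | t-test, simulated | Mann-Whitney, simulated |
|---|---|---|---|---|---|---|
| 0 | 1.00 | 1.000 | 1.00 | 5.0% | 5.0% | 5.0% |
| .05 | 1.10 | 1.048 | 1.02 | 5.6% | 5.5% | 5.5% |
| .10 | 1.19 | 1.096 | 1.05 | 6.1% | 6.1% | 6.0% |
| .20 | 1.38 | 1.191 | 1.09 | 7.3% | 7.3% | 7.2% |

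The simulations use a million null trials per row. At ICC .10 the 6.08% splits 3.07% in favour of hippotherapy and 3.01% in favour of the comparator.

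**Case 2: fixed trios of similar children, with no effect of riding together.** Twenty-three independent children are sorted into trios on a trait correlated .3, .5 or .7 with outcome. The within-trio ICC is then .09, .25 or .48, yet t-test error stays at 5.0% in all three settings. The arm mean is still a mean of 23 independent children, so correlated outcomes within a trio are not enough to cause inflation.

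**Case 3: trios that changed between sessions.** A per-session group effect that would give ICC .20 in fixed trios averages down to about .20/32 = .006, and the error is about 5.1%.

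**Case 4: fixed instructors.** Suppose each child stayed with one instructor, split 8, 8 and 7. Weighted group size = (64 + 64 + 49)/23 = 7.696, so DE = 1 + 6.696 × ICC = 1.07, 1.33 and 1.67 at ICC .01, .05 and .10. The approximate error is 5.4%, 7.0% and 9.0%, and simulation agrees.

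**What a group-level test would bring.** A Welch test of 8 riding-group means against 23 comparison children holds 5.0% in Case 1. In Case 2 it falls to 4.1%, 2.8% and 1.6%. Power at an assumed 0.8 SD effect:

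| Setting | t-test | Welch on group means |
|---|---|---|
| ICC 0 | 75.8% | 72.9% |
| Shared effect, ICC .10 | 74.8% | 68.6% |
| Similar children, correlation .3 / .5 / .7 | 75.6% each | 71.5 / 66.5 / 58.5% |

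At 0.8 SD and ICC 0, 6.5% of significant t-tests would lose significance under the Welch test although nothing is wrong with them. The data could not settle which analysis applies: with 8 groups the estimated ICC has a sampling SD of about 0.22, larger than any ICC assumed in Case 1.

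**The case for a change.** The strongest case for acting is that the text does describe group delivery, the named tests do ignore it, and the arithmetic is sound. A reader cannot tell from the plan whether .05 holds exactly, and a few sentences would help. The instructor route adds weight: with larger clusters, an ICC of only .05 gives about 7.0%. Nor are changing trios a complete safeguard. If shared session effects somehow kept a 20% share of outcome variance after 32 sessions, the error would be about 7.6%.

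The conditional arithmetic stands. What does not follow is that the plan contains an error. Each inflated figure needs stable groups or stable instructors, a causal effect of that sharing, and an average treatment effect of zero while some groups gain and others lose. If hippotherapy does nothing at all to anyone, the planned tests hold 5% even with fixed trios. The documents supply none of these conditions. Staff walking alongside the horse and individualized intensity point towards a small shared effect. The sentence on threes is also a loose account of delivery rather than a design structure: 23 does not divide by 3, and neither do 23 × 32 = 736 child-sessions.

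The natural remedy is also weak. A test on riding-group means needs attendance records that the documents do not mention. It is conservative if similar children were placed together, and it leaves most of the instructor route unrepaired (about 5.3%, 6.5% and 8.0% at ICC .01, .05 and .10). Losing significance on it could not by itself overturn the main result.

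**Conclusion.** No change to the planned analysis follows. The gap is one of descriptive detail: how riding groups and instructors were assigned, and whether they stayed the same. A trial report would ordinarily state this and mention possible clustering as a limitation. For fixed trios the possible inflation is 0.5 to 2.3 percentage points above .05 at an assumed ICC of .05 to .20. For fixed instructors it is about 0.4 to 4.0 points at an assumed ICC of .01 to .10. Both ranges rest on ICCs the documents do not give, an ungrouped comparison arm, and a zero average effect with real differences between groups. If children were only placed with similar children, there is no inflation. The t-test or Mann-Whitney test remains a reasonable main analysis for 46 children, and replacing or supplementing it with a test on riding-group means would cost power without resolving the question.

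### The only between-group analysis is an unadjusted t-test or Mann-Whitney U-test on an unspecified value; adjusting for baseline would cost little and usually gain precision

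*Combined protocol and SAP*

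**What the plan says.** The purpose section asks "whether hippotherapy improves the physical activity, cardiopulmonary fitness, and attention in children with cerebral palsy". The Statistical Analysis section is one paragraph. It works at one significance level, "using a .05 level of significance for all statistical tests", and checks normality with Shapiro-Wilk. On reporting it states: "Means and standard deviations are presented for each continuous variable". The between-group comparison follows the normality check and is a single clause: "the independent t-tests or Mann Whitney U-test were performed to examine the differences between the groups".

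On numbers, PARTICIPANTS states: "Forty-six children with CP (24 boys and 22 girls) participated in this study". INTERVENTION states: "23 children participated in the Hippotherapy program for 40 minutes per lesson twice a week for 16 weeks". On assignment it says only: "Children allocated in the Hippotherapy group participated the Hippotherapy program in indoor riding arena".

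No section names an outcome instrument, a baseline measurement or an assessment time. Sixteen weeks appears only as the length of the programme. No covariate, ANCOVA, mixed model or confidence interval for a group difference is mentioned.

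**The concern.** The clause on group differences fits a comparison of values after treatment, a comparison of changes, or even a comparison at entry. A reader cannot tell which was meant and so cannot reproduce the analysis.

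The first two readings estimate the effect differently whenever the groups differ at entry. For the t-test in the same children, the two mean differences differ by exactly the baseline gap. The Mann-Whitney test has no such identity, but its two readings also often disagree.

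Neither reading adjusts for baseline. With about 23 children per group and GMFCS levels I to III eligible, chance differences at entry are likely to matter. At stake are the precision of each comparison, its exposure to those differences, and a clear statement of what is being estimated.

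**Working it through.** The plan gives no power, effect size or SD, so there is no figure of its own to reproduce. What follows is an illustration.

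**Inputs from the documents.** Significance level .05; 46 children, 23 of them in hippotherapy.

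**Assumed.** 23 in the comparison group (46 − 23 = 23), two-sided testing, independent children, equal SDs, a normal outcome, a true difference d of 0.6 SD, and a baseline-outcome correlation r of .3, .5 or .7.

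**Formulas.** With n = 23 per group and outcome SD 1, the variance factor V is:
- post-treatment value: V = 1, df 44
- change: V = 2(1 − r), df 44
- ANCOVA: V = (1 − r²)(1 + 1/42), df 43; the last factor is the average cost of estimating the baseline slope

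Power comes from the noncentral t with noncentrality d√(n/2)/√V. Here d√(n/2) = 0.6 × √11.5 = 2.035. The 95% CI half-width is t(.975, df) × √(2V/23) and needs no effect size.

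**Example at r = .5.** For the post value and for change, V = 1, the noncentrality is 2.035 and power is 51%. For ANCOVA, V = 0.75 × 1.0238 = 0.768, the noncentrality is 2.035/√0.768 = 2.32 and power is 62%.

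| | r = .3 | r = .5 | r = .7 |
|---|---|---|---|
| Power, t-test on post value | 51% | 51% | 51% |
| Power, t-test on change | 39% | 51% | 73% |
| Power, ANCOVA | 54% | 62% | 79% |
| CI half-width, post (SD) | 0.59 | 0.59 | 0.59 |
| CI half-width, change (SD) | 0.70 | 0.59 | 0.46 |
| CI half-width, ANCOVA (SD) | 0.57 | 0.52 | 0.43 |

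**Range over effect size, same three correlations.**
- 0.4 SD: post 26%, change 20/26/40%, ANCOVA 28/33/45%
- 0.8 SD: post 76%, change 61/76/93%, ANCOVA 78/86/96%

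**Worst case for ANCOVA.** At r = 0 and 0.6 SD, ANCOVA has 50.2% against 51.2% for the post-value test. It breaks even with that test at about r = .16.

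**Chance imbalance under random allocation.** The baseline gap has standard error √(2/23) = 0.295 SD and exceeds 0.3 SD in 31% of trials. A gap b shifts the post-value difference by r·b and the change difference by −(1 − r)·b. With b = 0.3 and r = .5 these are +0.15 and −0.15 SD.

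**Do the two readings agree?** In simulation at 0.6 SD, exactly one of the post and change tests is significant in 31/34/39% of trials for the t-test and 32/35/40% for Mann-Whitney.

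**Skewed outcomes** (simulated, lognormal with log-SD 1, shift of 0.6 SD on the log scale):
- ANCOVA on the raw scale: 37/41/53%
- Mann-Whitney on the post value: 49%
- Mann-Whitney on change: 38/49/69%
- ANCOVA fitted to ranks: 52/59/73%, with error of about 5%; these values hold for any lognormal skew, because ranks do not change

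**The case against.** **The unadjusted tests are valid.** This stands if allocation was random: each single test then holds 5%. The case for adjustment is one of precision. A reader might infer an inflated error rate from the open choice between two readings. An error rate of about 9% would arise only if the more favourable reading were picked after seeing the data, and nothing in the documents suggests that.

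**The gain depends on figures the documents do not give.** Also true. If the intended test happens to suit r, the gain is modest. Against change it is 79 − 73 = 6 points at r = .7; against the post value it is 54 − 51 = 3 points at r = .3. Against the better of the two it is largest at r = .5, at 62 − 51 = 11 points. But r need not be known in advance: for a roughly normal outcome, ANCOVA is at or near the better unadjusted test at every r.

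**The plan already protects against non-normality.** This has force. ANCOVA on the raw scale loses to the plan's own Mann-Whitney test when the outcome is strongly skewed. That rules out raw-scale ANCOVA as the only test, and it is why the fix keeps the normality rule and moves to ranks.

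**The needed measurements are not described.** Correct, and this limits the remedy. ANCOVA needs a pre-treatment value, and that must be confirmed first. The wording of the purpose is compatible with a change analysis but does not settle the point.

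**Independence.** INTERVENTION says that children rode in groups of three. Any correlation within those groups would affect the adjusted and the unadjusted analyses alike, so all the figures above may be optimistic.

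**Conclusion.** The point holds as a cheap improvement to the analysis. The plan leaves its only between-group test undefined as to the value tested, and it does not use baseline. Under the stated assumptions ANCOVA adds 3 to 28 points of power over the post-value test (54 − 51 at r = .3; 79 − 51 at r = .7) and 6 to 15 over the change test (79 − 73 at r = .7; 54 − 39 at r = .3). It costs about 1 point if baseline explains nothing.

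Three stronger readings are not supported. The tests as written are not shown to be invalid. Selective choice between the two readings is not suggested by the text. ANCOVA would not rescue a non-random comparison: the document says only that children were allocated, and if allocation was not random, adjustment deals with imbalance in the measured baseline value alone.

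The missing statement of the tested value rests on the text and needs no assumption. The size of the gain rests on the assumed correlation, effect size, distribution, equal groups and independence.

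**What to change.** First confirm, and write into the plan, that each outcome was measured before treatment and at the end of the 16-week programme. Then replace the between-group sentence with, in substance:

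- **Primary comparison.** For each such outcome, ANCOVA of the end value on group and the baseline value of the same outcome. Report the adjusted mean difference with its model-based 95% CI.
- **Normality rule, kept.** If the residuals fail Shapiro-Wilk (p < .05), the test is taken from the same model fitted to ranks, in place of the Mann-Whitney U-test.
- **Sensitivity analysis.** The unadjusted test on change from baseline: t-test if Shapiro-Wilk p ≥ .05 in both groups, otherwise Mann-Whitney.

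A bootstrap interval should not be added for non-normal residuals. A second interval leaves open which one governs, and in simulation, substituting it for the model interval raised the error to 6.1–7.5% for skewed outcomes. Adjustment for GMFCS level can be an optional further analysis; its gain cannot be computed from the documents.

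The cost is one standard linear model per outcome and one degree of freedom. A rank-based result also carries no mean difference on the original scale.

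The section is written in the past tense. If the data had already been analysed, keep the t-test and Mann-Whitney results, state which value they tested, and add the ANCOVA labelled as not prespecified.
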